- 2) Examine whether enhanced STOMP messaging will mitigate persistent/recurrent opioid use and later misuse among older adolescents and emerging adults. We hypothesize that opioid misuse risk perceptions mediate the relationship between prescription opioid use and later misuse, and that by enhancing risk perceptions, rates of opioid misuse intentions will decrease.

With adequate funding, we have the unique ability to expand and test translatable strategies that could effectively mitigate adverse outcomes related to opioid prescribing. Our multidisciplinary team's expertise related to opioid risks and pain management practices for youth and opioid misuse, combined with our ability to efficiently recruit and retain research subjects in clinical studies (current loss-to-follow-up is < 15%) supports the natural extension of our current project and will ensure completion within the timeframe of our current grant. This additional work will not only increase the impact of our research, but will lay the necessary foundation for a future longitudinal study of prescription opioid misuse among adolescents and emerging adults.

SIGNIFICANCE OF THIS SUPPLEMENT

Adolescents and emerging adults, themselves, are vulnerable to opioid-related adverse outcomes given high rates of pain and exposure to prescribed opioids. More than 90% of healthy youth report recent pain for which most have self-treated with analgesics.¹³⁻¹⁵

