Poor analgesic and opioid risk knowledge and perceptions contributes to risky misuse behaviors among adolescents and emerging adults. We recently surveyed 972 healthy community youth aged 15-24 years of age and found that nearly half had taken a prescribed opioid for pain and of these, 32% reported past misuse (i.e., taking more of the drug, taking it more frequently, or using it for an unrelated condition) and 26% indicated a willingness to misuse a prescribed opioid to manage pain.⁹ Similar to findings from our studies of parents, we demonstrated that intentions to misuse a prescribed opioid were strongly associated with lower perception of opioid misuse risk and stronger preferences for analgesic benefit or pain relief (vs. analgesic risk avoidance). We also found that past opioid misuse experience helped explain opioid misuse intentions. Importantly, we found no association between simple awareness of serious opioid-related adverse outcomes (e.g., addiction, excessive sedation, respiratory depression) and willingness to misuse a prescription opioid.

Other studies of risky decision-making have demonstrated that adolescents and young adults respond more to the possibility of short-term benefit or reward (such as pain relief or other effects) than to the potential long-term and rare risks (such as addiction).³³ College students also assign less risk to prescription analgesics than to other substances, and perceived harm is highly associated with higher risk of nonmedical misuse.^{34,35} These data may be, in part, explained by risk reappraisal that occurs after prescription analgesic use (or misuse), in that

experience with positive benefits and no adverse outcomes may lead to downward reappraisal of riskiness.³⁶ Together, such data indicate a critical need to enhance prescription opioid risk perceptions and pain management understanding at the time of initial exposure and prior to risk reappraisal.

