Our multidisciplinary team brings expertise in acute post-procedure pain management, adolescent substance use behaviors (with a particular emphasis on prescription opioid misuse among adolescents and emerging adults),^{10,11,22,26,28,43} tailored decision-aid technology and evaluation of educational and behavioral interventions in the clinical setting.⁴⁴⁻⁴⁷ Increasing [name] effort from a consulting role to an active co-investigator will bring a more prominent role regarding effective pain management strategies and interpretation of data.

APPROACH

With this supplement, we aim to expand the target population identified in our parent study to include older adolescents and emerging adults (ages 15-24 years) who are beginning to or are solely making analgesic decisions for themselves following a painful procedure.

We will adapt STOMP messages to specifically address the risks of personal misuse of opioid analgesics and the potential risk of sharing prescribed opioids with others. We will modify the analgesic messages that address safe and effective pain management strategies and early opioid weaning.

Using modified surveys but similar procedures as the parent project, we will test the effect of STOMP on the outcomes: opioid risk perceptions, misuse intentions and behaviors, persistent use and left-over disposal intention.

Expanded sample inclusion and justification: We will recruit up to 600 English speaking patients, aged 15-24 of all races who are expected to receive an opioid prescription for acute, short-term postoperative pain following elective ambulatory or short stay (<48 hrs) orthopedic, sports medicine, or other surgical procedures.

Sample exclusions: We will exclude patients who are undergoing emergency procedures, cannot self-report their pain, have a hematologic-oncologic, kidney or liver condition (precluding the usual analgesic prescription patterns), or who have been recently treated for chronic pain. We will exclude subjects with significant mental health history that includes diagnoses with treatment for severe depression, bipolar disorder, psychoses, suicidal ideation.

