- **Surgical factors:** The procedure, prior injury, duration of surgery, all perioperative analgesics given and details of participant's prescription and analgesic instructions will be recorded from the medical record.

Study Procedures (SEE TABLE 1 BELOW)

Group assignment: Participants will be randomly assigned a priori by computer generated randomization to one of the three groups: the Control Group (i.e., Routine provider

pen/verbal analgesic instruction), the STOMP written feedback (intervention) Group: (i.e., Routine provider information plus the STOMP written feedback) or the enhanced STOMP Video Feedback (intervention) Group (i.e., Routine provider information plus the STOMP Video feedback).

All baseline and follow-up surveys are completed by the subjects using a Qualtrics survey link via their own smartphone or computer (or our iPad if completed in person) to ensure completeness and privacy. Subjects will enter only an assigned, unique ID number with no other identifying information. STOMP (either written or video groups) will be provided together with each decision exercise (built into the survey itself). The electronic survey includes appropriate logic and prompts to minimize the potential for missing items.

Subjects will be texted/emailed survey links on day 0 (day before or on surgery), day 7, day 14, 1 & 3 months after discharge. Table 1 depicts the study assessments completed at each timepoint. These will be automatically scheduled via our umich gmail system. On each of the survey days, we will also send a text SMS reminder to participants (automated using the same process as our parent study). Subjects can opt to complete surveys via email link (Qualtrics) or via paper/pen (returned via mail). No more than 1 additional text reminder for each will be sent to subjects who have not completed their follow-up surveys.

Sample Size Determination

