Our sample size is based on our recent findings that 26% of adolescents/young adults indicated a willingness to misuse a prescribed opioid for pain management. We need 426 participants (142/group) to detect a clinically important effect of the STOMP intervention on misuse intention (i.e., decrease to 13%; 95% confidence and 80% power). This sample will be more than sufficient to detect an expected mean difference in opioid misuse risk perception between either intervention group and the control (MD 0.56, SD 1.21; sample needed = 122) and to test for a modest effect of the interventions in a factorial design (estimated eta squared 0.14; sample needed = 147). To allow for 30% loss to follow-up and to account for missing data, we will recruit up to 600 participants.

Table 1. Sequence of study assessments

Measures	Time 0 Baseline (preop)	Time 0.1 (Immediately Post-Session)	Time 1 (7 days)	Time 2 (14 days)	Time 3 (1 month)	Time 4 (3 months)
Demographics	x					
Pain, Analgesic and Misuse History	x					
Pain relief Preference	x			x		
Opioid knowledge/ risk perceptions	x	x		x	x	x
Opioid misuse risk perceptions	x	x		x	x	x
Scenario (situational) decision-making	x			x	x	x
Analgesic self-efficacy	x	x				
Pain interference			x	x	x	x
Opioid left-over disposal				x	x	x

Analgesic use and ADEs			x	x	x	x
Perioperative data	x					
Analgesic refill data				x		

DATA ANALYSES

Generalized estimating equations (GEE) will be used to model both continuous (i.e., negative binomial and Gaussian) and binary outcomes (i.e., binomial) for each aim.^{151,152} All models will include both time-varying measures (e.g., opioid risk perceptions) and time-invariant covariates (e.g., sex, race, etc.) and will use either an independent or exchangeable correlation structure to correct for within subject correlations. Analyses will use Stata's (STATA/SE v.13; STATA Corp., College Station, TX) 'xtgee' option as appropriate. All hypotheses per our conceptual model (Figure 3) will be tested at the 0.05 alpha level. Standardized coefficients and adjusted odds ratios will be computed to determine the relative effect size for each of the key independent variables.

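### Aim 2's mediation hypothesis takes non-randomised opioid use as its exposure, so as worded it cannot show that STOMP works through risk perceptions, and no analysis of that pathway is specified

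*Combined protocol and SAP*

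**What the plan says.** Specific Aims, Aim 2, opens with a question about the intervention: "Examine whether enhanced STOMP messaging will mitigate persistent/recurrent opioid use and later misuse among older adolescents and emerging adults". The hypothesis beneath it has two clauses. The first is "We hypothesize that opioid misuse risk perceptions mediate the relationship between prescription opioid use and later misuse". The second continues "and that by enhancing risk perceptions, rates of opioid misuse intentions will decrease".

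Under Study Procedures, Group assignment, the randomised factor is the message group: "Participants will be randomly assigned a priori by computer generated randomization to one of the three groups" (control, STOMP written, STOMP video). Under Expanded sample inclusion and justification, eligible patients are those "who are expected to receive an opioid prescription for acute, short-term postoperative pain". Under Measurements, Analgesic adherence, consumption is recorded as an amount (mg/kg), as a percentage of the doses prescribed, and as left-over doses.

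Data Analyses begins "Generalized estimating equations (GEE) will be used to model both continuous" and binary outcomes, for each aim. It adds that every model will contain time-varying measures, with opioid risk perceptions as the example, plus fixed covariates. Only Aim 1 then has its own paragraph. There, randomised group is the independent variable, in main-effect and time-by-group models of perceptions and decisions. No Aim 2 model, indirect effect, or covariate set for mediation appears. The Outcomes list for Aim 2 names persistent use and left-over retention, but not later misuse.

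**The concern.** The rationale, set out under Scientific Premise and in the account of Fuzzy Trace Theory, is that STOMP changes behaviour by raising perceived risk. To test this, randomised group must be the exposure. The first clause of the hypothesis makes opioid use the exposure instead, so randomisation protects no part of the tested path.

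The Significance section itself supplies both threats to that path. Pain relief is described as the commonest motive for misuse, and a stronger preference for pain relief is linked to misuse intention, so both are candidate common causes. Direction is also unclear, because "experience with positive benefits and no adverse outcomes may lead to downward reappraisal of riskiness": use or misuse may change perceptions, rather than perceptions changing misuse. A positive result could be reported as support for STOMP's mechanism when it is not. The randomised Aim 1 comparisons do not rest on this hypothesis.

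**Working it through.** **1. The plan's own figure.** Sample Size Determination gives 142 per group for 26% v 13%. With two-sided alpha 0.05 (sidedness assumed) and 80% power, unpooled:

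n = (1.960 + 0.842)² × (0.26×0.74 + 0.13×0.87) / 0.13² = 7.849 × 0.3055 / 0.0169 = 141.9, so 142.

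It is reproduced. It powers the total effect on intention; no figure is given for mediation.

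**2. Two readings of the exposure.**

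| Reading of opioid use | Does it vary? | Randomised? | Consequence |
|---|---|---|---|
| Being prescribed an opioid | Hardly, by eligibility | No | Mediation cannot be estimated |
| Amount or duration taken | Yes | No; arises after randomisation | Estimable, but confounded |

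Neither reading shows that STOMP acts through perceptions.

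**3. Timing in Table 1.** Misuse risk perceptions: Time 0, Time 0.1 (immediately post-session), 14 days, 1 month, 3 months. Scenario decisions: Time 0, 14 days, 1 month, 3 months. From 14 days on the two are measured together, so same-visit associations have no direction. Time 0.1 perceptions come before every follow-up decision. They also come before postoperative opioid use, because STOMP is built into the survey completed before surgery.

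**4. False positives for the opioid-use hypothesis.** Simulated trials, n = 420 (600 × 0.70), no true effect of use or perception on intention, one shared pain/preference factor, joint-significance test at 0.05. The loadings are assumptions.

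| Adjustment | Loading 0.3 | 0.5 | 0.7 |
|---|---|---|---|
| None (range over scalings) | 5-11% | 59-85% | 94-99% |
| Imperfect baseline covariates | 8% | 62% | 91% |
| Shared factor fully adjusted | 0.4% | 0.5% | 0.1% |

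The error rate depends on how fully the covariates capture the shared factor.

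**5. Which mediator time for the STOMP pathway?** Suppose a factor arising after Time 0.1, such as postoperative pain, loads L on both 14-day perception and 3-month intention, with unit variances and no true perception effect. One STOMP arm v control, N = 284.

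- Group to perception: 0.56/1.21 = 0.463 SD; 0.463 × √(142/2) = 3.90; power = Φ(3.90 − 1.96) = 97.4%.
- The spurious perception-intention correlation is L². Its test statistic is atanh(L²) × √(284 − 1 − 3).

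| L | L² | Statistic | Rejection | × 0.974 |
|---|---|---|---|---|
| 0.3 | 0.09 | 1.51 | 33% | 32% |
| 0.5 | 0.25 | 4.27 | 99% | 96% |
| 0.7 | 0.49 | 8.97 | 100% | 97% |

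Simulation agrees to within about a percentage point. A Time 0.1 mediator cannot be affected by that factor, so its rate is 0.05 × 0.974 = 4.9%.

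Baseline confounding is a separate matter and can affect Time 0.1 as well. With imperfect baseline covariates, STOMP-pathway simulations gave false positives of about 12-21%, 46-68% and 91-92% at loadings 0.3, 0.5 and 0.7. With the shared factor fully adjusted they gave 4-5%.

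**6. Joint power for the STOMP pathway.** 142 per arm, control rate 26%, active rate held at 13% by a direct effect, 1,000 runs each. The perception-to-intention odds ratio (OR) is not in the documents, so a range is assumed.

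| OR per SD | Active rate from indirect path alone | Joint power |
|---|---|---|
| 0.9 | 25.1% | 11% |
| 0.8 | 24.1% | 28% |
| 0.7 | 23.0% | 62% |
| 0.6 | 21.9% | 86% |
| 0.5 | 20.7% | 96% |

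Even at OR 0.5 the indirect path accounts for 26 − 20.7 = 5.3 of the 13 points.

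**The case against.** The best defence is that the pathway of interest is already present. The second clause, "and that by enhancing risk perceptions, rates of opioid misuse intentions will decrease", loosely describes it, since STOMP is what enhances perceptions. Aim 1 tests group on perceptions and group on decisions, both with randomised group as the independent variable. This stands, and it narrows the gap to a missing indirect effect. But the clause names neither group as the exposure nor an analysis, and two separate group effects do not establish that one carries the other.

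A reader might infer that the exposure is constant, so that nothing can be estimated. The documents do not support this. They select on an expected prescription, not on equal use; use is recorded as a quantity, and persistent use is an outcome. On that reading the exposure is confounded, not absent.

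A reader might also infer that the trial cannot study STOMP's mechanism at all. That too is unsupported: group is randomised, and Table 1 measures perceptions at Time 0.1, before the follow-up decisions. The fault lies in the wording and the missing analysis, not in the design or data.

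A third tempting reading is that using randomised group as the exposure removes the bias. It does not: step 5 shows high error rates when baseline covariates capture the shared factor poorly. Comparing an unadjusted opioid-use model with an adjusted STOMP model would overstate the gain, since the plan puts covariates in all its models.

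Finally, Data Analyses refers to a conceptual-model figure that is not shown, and much detail is left to the parent project. The pathway may be drawn there, but a diagram would not supply an estimand or covariate set.

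**Conclusion.** The point holds. As worded, Aim 2's mediation hypothesis addresses a non-randomised, post-randomisation exposure (or one that barely varies), so it cannot show that STOMP works through risk perceptions. No analysis in the available text estimates that indirect effect. The structural finding rests on the wording alone. The size of the bias rests on assumed loadings and scaling: false-positive rates for the opioid-use hypothesis run from under 1% with complete confounder adjustment to 90% or more with strong, poorly measured confounding.

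The remedy improves the question asked and, with a Time 0.1 mediator, excludes postoperative confounding of the mediator. It leaves the perception-to-intention step observational. The 97% power for the first step assumes that the stated difference of 0.56 (SD 1.21), given without a time point, applies at Time 0.1. This should be corrected, but it does not threaten the randomised comparisons, and any mediation result should be labelled secondary.

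**What to change.** - **Hypothesis.** Restate it as: randomised STOMP group affects misuse intention at 14 days to 3 months through misuse risk perception measured immediately post-session (Time 0.1). Keep 14-day perception as a secondary mediator only.
- **Estimation.** Prespecify direct and indirect effects with bootstrap intervals. Adjust for Time 0 perception, PR-Pref, past misuse, and Time 0 decisions recorded before any STOMP feedback. The last condition matters because feedback is delivered with each decision exercise, so later Time 0 scenarios may already reflect it.
- **Sensitivity analysis.** Include one for unmeasured mediator-outcome confounding. Given step 5, it is essential.
- **Total-effect models.** Leave post-randomisation perceptions out of the models for the total effect of group on decisions. Read literally, Data Analyses puts them in every model, which would adjust away part of the effect of interest.
- **Opioid-use associations.** Report any link between amount used, perceptions and misuse as observational.

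The cost is a rewording of Aim 2 and one added analysis. Perceptions, decisions, PR-Pref and misuse history are all in Table 1, so no new measure is needed; the survey data must let pre-feedback decisions be identified. The drawbacks are an untestable assumption at the mediator-outcome step and uncertain power, both of which should be stated with the result.

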Protection against risk (see Parent Protection of Human Subjects for more detail): Our opioid messages are developed with the guidance of pediatric pain and risk communications experts. The intervention poses no more than minimal risk to adolescents or young adults but may instead, offer potential benefit in terms of risk reduction, self-efficacy and pain management competency.

We will minimize the risk for breach of confidentiality of all participants by training of study team members, use of electronic and physical security measures for data capture and storage, and by employing a Certificate of Confidentiality (automatic for NIH funded studies). Unique study identifiers (ID) for each subject will permit linkage between surveys and follow-up data while maintaining the privacy of every participant. ID links between subjects and their data will be kept separately in an encrypted file. Data will only be stored on fire-walled databases which will limit access only to those assigned appropriate permissions.

Routine management will not be altered and we will exclude those who cannot, by nature of their underlying condition be safely prescribed the usual combination of opioids and non-opioids for postoperative pain. We will record all adverse events and will review non-serious AEs

quarterly and serious AEs as they are learned to determine the relationship to study participation and actions needed, if any (see DSMP).

Data and safety monitoring plan (DSMP): Our study specific DSMP provides details of how we will collect, review, evaluate and manage adverse events that may happen as part of routine care or study participation.

Group assignment (same as parent study): Patients will be randomly assigned a priori by computer generated randomization to either the Control Group (i.e., Routine provider written/verbal analgesic instruction) or one of two Intervention Groups: STOMP written (prose) feedback (i.e., Routine provider information plus the STOMP written feedback or our enhanced STOMP Video feedback (i.e., Routine provider information plus STOMP Video feedback).

Outcomes

Aim 1) Opioid risk perceptions, misuse risk perceptions, intentions to medically misuse, non-medically misuse or divert left-over opioids

Aim 2) Persistent opioid use after surgery, left-over opioid retention

Measurements (only modifications from parent grant are described)

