Missing data: The use of electronic surveys with built-in prompts for incomplete items will reduce the potential for missing responses. Patients will be contacted by phone, text or email (per their preference) to promote ongoing recording of postoperative data and to reduce the potential for missing data and LTF. We have used similar procedures to successfully ensure complete data and minimize loss to follow-up.^{8,25,94,153}

Any remaining missing data on surveys (e.g., assist or PR-Pref) will be examined for randomness and we will impute only partial non-response (e.g., missing 1 to 2 items of PR-Pref or assist) using a horizontal (i.e., per individual) approach. Largely incomplete or total survey non-response will be examined for non-randomness and potential bias (e.g., missing DAST-10). These missing data will not be imputed, however, outcomes will be compared for persons with missing vs. complete data to determine selection bias. We have adjusted our sample size to account for the potential for missing data. We will use pairwise deletion to use the available, complete cases to test our hypotheses.

Aim 1: Using GEE, we will examine the association between the STOMP intervention and the outcomes (risk seriousness perception, and situational opioid decisions). It is hypothesized that, compared to controls, patients who receive the STOMP intervention will have 1) enhanced risk perceptions (continuous measure) and 2) improved opioid decisions (scenario-based). Hypotheses 1 and 2 will be tested using both main and interaction effect models. In the main effects models, STOMP group assignment is our binary independent variable of interest. Time by intervention interaction effect models will be used to examine whether the STOMP group has improved opioid risk perceptions and decisions at the follow-up assessments compared to the control group. It is expected that there will be no difference between the intervention group and control group at baseline. However, significant interaction effect terms should emerge for the intervention group at the follow-up assessments.

Anticipated Problems and Solutions:

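### Aim 2 claims that risk perceptions mediate later misuse, but the plan sets no time order between perception and outcome, so a same-visit association could not support the claim

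*Combined protocol and SAP*

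**What the plan says.** Aim 2 in the Specific Aims is a statement about order in time: "We hypothesize that opioid misuse risk perceptions mediate the relationship between prescription opioid use and later misuse". It goes on to expect that enhancing perceptions will reduce misuse intentions.

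The Data Analyses section specifies GEE models fitted with xtgee and tests all hypotheses at the 0.05 level. On the predictor side it says: "All models will include both time-varying measures (e.g., opioid risk perceptions) and time-invariant covariates (e.g., sex, race, etc". No lag is given. The Aim 1 paragraph also uses perceptions as an outcome: "we will examine the association between the STOMP intervention and the outcomes (risk seriousness perception, and situational opioid decisions". There is no Aim 2 analysis paragraph, mediation model or indirect effect. The Outcomes list reads "Aim 2) Persistent opioid use after surgery, left-over opioid retention" and names neither later misuse nor a mediator.

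Table 1 schedules the relevant readings as follows:

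- misuse risk perceptions: Time 0, Time 0.1, 14 days, 1 month and 3 months;
- scenario decisions: Time 0, 14 days, 1 month and 3 months;
- analgesic use: 7 days, 14 days, 1 month and 3 months;
- misuse history: Time 0 only.

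The Significance section partly explains known links between perceived harm and misuse by "risk reappraisal that occurs after prescription analgesic use (or misuse", bracket left open by the cut. It adds that "experience with positive benefits and no adverse outcomes may lead to downward reappraisal of riskiness".

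**The concern.** A mediator has to be measured after the exposure and before the outcome it is said to influence. If the value entered comes from the outcome survey, a low perception beside a risky decision fits two stories. Perception may have shaped the decision, or misuse since the last survey may have lowered the perception and also made the risky answer more likely. The Significance section supports the second route. It says reappraisal can follow misuse, and it reports that past misuse experience helped explain misuse intentions.

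At stake is the Aim 2 conclusion that raising perceptions is what lowers misuse. The one specified tool could return a clearly significant perception coefficient when perceptions have no effect.

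**Working it through.** **The plan's own figure.** With 26% against 13%, two-sided 0.05 and 80% power (unpooled variance), n per group = (1.960 + 0.842)² × (0.26×0.74 + 0.13×0.87) / 0.13² = 7.849 × 0.3055 / 0.0169 = 141.9. This matches the stated 142 per group and is not in dispute. The Sample Size section gives no figure for mediation.

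**Inputs from the plan.** Up to 600 recruited less 30% loss leaves 420, or 140 per arm. Intention rates are 26% in control and 13% in the two STOMP arms. The perception SD is 1.21.

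**Assumed inputs, not in the documents.** Perception has no true effect on the outcome. A positive outcome lowers the same-visit rating by d SDs.

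**One-visit model: outcome on arm and same-visit perception.**

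- False log odds ratio per point = −d/1.21, so the odds ratio = exp(−d/1.21).
- Information for the perception term (perception in SD units) = 140×0.26×0.74 + 280×0.13×0.87 = 26.94 + 31.67 = 58.6. The standard error = 1/√58.6 = 0.131.
- z = d/0.131. Two-sided rejection rate = Φ(z − 1.96) + Φ(−z − 1.96).

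| d (SD) | False OR per point | z | False-positive rate |
|---|---|---|---|
| 0 | 1.00 | 0 | 5% |
| 0.1 | 0.92 | 0.77 | 12% |
| 0.25 | 0.81 | 1.91 | 48% |
| 0.5 | 0.66 | 3.83 | 97% |

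Two separate simulations of this design gave 48% and 43% at 0.25 SD and 96% each at 0.5 SD. One of them also covered 0.1 SD and gave 12%.

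**Three visits pooled.** This used a logistic GEE with independence working correlation and robust standard errors, 420 participants without an arm effect and 200 replicates. Two further assumptions are a within-person perception correlation of 0.7 and a propensity SD of 1 on the logit scale. The table counts significant results in the protective direction only, where the nominal rate is 2.5%. Monte Carlo error is about 1 to 3.5 percentage points.

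| Reverse effect (SD) | Same visit | Prior visit, unadjusted | Prior visit, adjusted for prior outcome |
|---|---|---|---|
| 0 | 1.5% | 3.5% | 2% |
| 0.1 | 32% | 3% | 1.5% |
| 0.2 | 84.5% | 5.5% | 2% |
| 0.3 | 98% | 5.5% | 3.5% |
| 0.5 | 100% | 8.5% | 3% |

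The lag removes most of the false signal, and adjusting for the preceding outcome removes the rest.

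**The case against.** The strongest reply is that the plan describes no mediation estimate. Perceptions appear in the Data Analyses section as one example in a generic sentence. Nothing says their coefficient will be interpreted as mediation, and same-visit use is inferred from silence. The conceptual figure cannot be seen, and the supplement leans on a parent protocol that is not in hand. All of that stands. A reader might infer that the plan would report reverse causation as mediation. The documents do not go that far: the hypothesis has one available tool, and that tool has no time order.

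Three other stronger readings also fail.

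- A reader might infer that perceptions serve only as a covariate. They are also an Aim 1 outcome compared between randomised groups, and this reverse path does not bias that comparison.
- A reader might infer that opioid use lowering perceived risk is itself reverse causation. Under Aim 2 it is the first leg of the proposed pathway. Only the mention of misuse supplies a path from outcome back to mediator, and the reappraisal statement is hedged with may.
- A reader might take the percentages as rates expected in this trial. The 26% and 13% are scenario-based intentions, whereas the reappraisal described follows actual drug experience. For an intention outcome, recent misuse would have to act on both answers, so the effective link could be weaker than the values assumed.

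**Conclusion.** The concern holds in limited form. Aim 2 makes a time-ordered claim, and the plan gives perceptions no lag, so following it as written cannot separate perception lowering misuse from misuse lowering perception. The error could be large. False positives in a one-visit model run from about 12% at an assumed reverse effect of 0.1 SD to about 97% at 0.5 SD, and they rise faster when visits are pooled. These figures show sensitivity to an assumption and are not a forecast. They rest on reading the unlagged covariate as the same-visit value, on no true perception effect, and on the outcome acting directly on the rating. The randomised comparisons of STOMP with control on perceptions and decisions are not challenged here. The change should be made before analysis, because a lag chosen after the data are seen carries less weight.

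**What to change.** Add an Aim 2 mediation paragraph that uses a perception reading taken after the exposure and before the outcome.

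- **Opioid-use path:** use reported through 14 days, perception at 14 days, outcome at 1 month; then perception at 1 month with outcome at 3 months. Time 0.1 is unsuitable here, because it precedes postoperative opioid use and so cannot mediate its effect.
- **STOMP path:** the same pairs, and Time 0.1 perception with the 14-day outcome may also be used.
- **Adjustment:** the outcome at the preceding decision visit (Time 0 for the 14-day outcome) and Time 0 perception.
- **Reporting:** same-visit associations as descriptive only.
- **Outcome:** state that it is scenario-based misuse intention unless a follow-up misuse measure is named, since Table 1 has no follow-up row for actual misuse.

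The cost is plan wording and lagged variables. Table 1 already schedules the perception, decision and analgesic-use readings, so an intention outcome needs no new data collection. The downside is that a participant who misses the preceding survey does not contribute to that pair. Lagging also does not remove confounding by unmeasured causes of both perception and outcome, and the paragraph should say so.
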